### 13.4. Institutional Review Board or Ethics Committee

In accordance with 21 CFR 56, the protocol, advertisement, and Informed Consent Form (ICF) and assents will be reviewed and approved by the IRB or EC. The Sponsor will supply relevant material for the Investigator to submit to the IRB/EC for the protocol's review and approval. Verification of the IRB/EC unconditional approval of the protocol and the written ICF/assent statement will be transmitted to the Investigator.

The IRB/EC will be informed by the Investigator(s) or their representative(s) of subsequent protocol amendments and of serious and unexpected AEs. Approval for protocol amendments will be transmitted in writing to the Investigator. If requested, the

Investigator(s) or their representative(s) will permit audits by the IRB/EC and Regulatory inspections by providing direct access to source data/documents.

The Investigator(s) or their representative(s) will provide the IRB/EC with progress reports at appropriate intervals (not to exceed one year) and a Study Progress Report following the completion, termination, or discontinuation of the Investigator(s)' participation in the study.

### **13.5. Patient Insurance**

If applicable, patient insurance will be secured according to national or local requirements. Where applicable, the name and address of the relevant insurance company, the certificate of insurance, the policy number and the sum insured will be provided in the Investigator's File.

### **13.6. Informed Consent and Assent**

Written informed assent for the study will be obtained from all pediatric patients and informed consent will be obtained from their parents or legal guardian before protocol-specific procedures are carried out. The ICF/assents generated by the Investigator(s) or their representative(s) will be approved (along with the protocol) by the IRB or EC and will be acceptable to the Sponsor.

The Investigator(s) or their representative(s) will explain the nature of the study and the action of the test product.

The patient (or parent) will be informed that participation is voluntary and that they can withdraw from the study at any time. In accordance with 21 CFR 50, the informed consent process shall be documented by the use of a written ICF approved by the IRB or EC and will be signed by the subject prior to protocol-specific procedures being performed. The consent process will be completely documented in each subject's source record.

The patient (or parent) will be given a copy of the signed consent, and the original will be maintained with the patient's records.

### **13.7. Records**

The results from Screening and data collected during the study will be recorded in the patient's CRF (either paper or electronic CRF). To maintain confidentiality, the patients will be identified only by numbers and/or initials.

If applicable, the completed CRFs will be transferred to the Sponsor or designee and copies of each CRF will be retained by the Investigator. All source documents, records, and reports will be retained by the study site in accordance with 21 CFR 312.62(c). All primary data, or copies thereof (e.g., laboratory records, CRFs, data sheets, correspondence, photographs, and computer records), which are a result of the original observations and activities of the study and are necessary for the reconstruction and evaluation of any study report, will be retained in the study site archives.

### **13.8. Quality Control and Quality Assurance**

Accurate, consistent and reliable data will be ensured through the use of standard practices and procedures. Experienced clinical research associates (CRAs) will monitor the Investigators' source data against eCRF entries and verify that the data is accurate.

### **13.9. Archiving of Data**

Patient files and other source data shall be kept for the maximum period of time permitted by the hospital or institution. The Investigator shall retain the trial related essential documents until the Sponsor informs the Investigator these documents are no longer needed. All data and documents shall be made available at the request of relevant authorities. The Investigator shall inform the Sponsor before any records are destroyed.

## 15. Appendices

### 15.1. INSTRUCTIONS FOR CALCULATING BMI/BSA

- Screening height will be used for all body mass index (BMI) calculations. The formula for calculating BMI is:

$$BMI = \text{weight (kg)} \div \text{height (m)}^2$$

Example: The BMI of a subject 1.7 m tall who weighs 90 kg is:

$$BMI = 90 \div 1.7 \text{ m}^2 = 31.1 \text{ kg/m}^2$$

- To calculate body surface area, or BSA in ( $\text{m}^2$ ) the method of Haycock is being used [Haycock GB, *et al*, 1978]

$$m^2 = [\text{Height (cm)}^{0.3964} \times \text{Weight (kg)}^{0.5378}] * 0.024265$$

Note: 2.2 lb = 1 kg; 1 in = 0.0254 m = 2.54 cm

## 15.2. PHARMACOKINETIC SAMPLE COLLECTION & PROCESSING

### 15.2.1. PK Sample Collection

For the analysis of plasma cysteamine, approximately 2 mL of blood will be collected in chilled (+2°C to +8°C) in a 2mL green-top evacuated collection tube containing sodium heparin.

Each PK sample tube label must include the protocol number, 5-digit subject ID number, collection date and nominal collection time.

After collection, tubes will be mixed by gently by inverting 2 to 3 times and stored in an ice water bath until they are centrifuged (i.e., within 1 hour of collection).

### 15.2.2. PK Sample Processing

Within 1 hour of collection, PK blood samples will be centrifuged at 2000g and 4°C for at least 10 minutes. The plasma will be split into two approximately equal volumes and placed into two different cryotube vials (one for PK analysis, and one back-up) and frozen at approximately -70°C or below.

Cryotube vials will be properly stored at approximately -70°C or below until shipment to the central laboratory. Each cryotube label must include the protocol number, 5-digit subject ID number, collection date, nominal collection time and the tube number (e.g. PK sample "1 of 2").

The two PK sample aliquots will be shipped to the laboratory in two different shipments (in case one is lost in transit), with sufficient dry ice to last the duration of transit.

## **15.3. PHARMACODYNAMIC SAMPLE COLLECTION & PROCESSING**

### **15.3.1. PD Sample Collection**

For analysis of the PD biomarkers, approximately 2 mL of whole blood will be collected for glutathione and glutathione-disulfide testing and 2 ml will be collected for lactate testing using the tubes provided.

Each sample tube label must include the protocol number, subject ID number, collection date and nominal collection time.

After collection, tubes will be mixed gently by inverting 7-8 and 8-10 times, respectively.

### **15.3.2. PD Sample Processing**

PD blood samples will be prepared and stored as described in the central lab manual (or Study Reference Manual).

#### 15.4. RP103 DOSING INSTRUCTIONS

##### RP103 DOSE AND FOOD TIMING

- Subjects should not eat for at least 2 hours before taking and at least 30 minutes after taking RP103.
- Subjects who are unable to take RP103 without eating should eat only a small amount (approximately 4 ounces or  $\frac{1}{2}$  cup) of food between 1 hour before and 1 hour after taking RP103.
- Dairy products should be withheld between 1 hour before and 1 hour after taking RP103.

##### RP103 DOSING IN FOOD

Below are instructions for subjects unable or unwilling to take whole, intact RP103 capsules and prefer to dose in food.

###### OPTION 1 – EATING:

- Open all the capsules for either the morning or evening dose and sprinkle the contents onto approximately 4 ounces of an acceptable soft food.
- Gently stir the medication beads into the soft food, creating an RP103-food mixture.
- Eat the entire amount of RP103-food mixture. This may be followed by 8 ounces (1 cup) of an acceptable liquid.

###### OPTION 2 – ADMINISTRATION BY G-TUBE:

- Open all the capsules for either the morning or evening dose and sprinkle the contents onto approximately 4 ounces of applesauce (NOT liquid).
- Gently stir the medication beads into the soft food, creating an RP103-applesauce mixture.
- Place the syringe tip at the bottom of the container of RP103-applesauce mixture; draw up a third of the mixture.
- Keeping the syringe tip at the bottom of the container, mix for a few seconds, then draw up another one-third of the RP103-applesauce mixture. Repeat this step and draw up the final one-third of the RP103-applesauce mixture. This method prevents air from entering the syringe.
- Place syringe on the feeding tube (G-tube only; do not use GJ- or NG-tube) and slowly dispense until the RP103-applesauce mixture is at the end. This removes any air from the tube.
- Place the tube on the button. Deliver the RP103-applesauce mixture at a rate of 10mL/10 seconds, until the syringe is fully dispensed into the tube.
- Take a syringe of acidic juice or other acceptable liquid and deliver through the tube to ensure the entire RP103-applesauce mixture has been administered into the body, and no beads are left in the tube.

\* *The RP103-food/RP103-applesauce mixture must be eaten or administered within 2 hours after preparation.*

## RP103 DOSING IN LIQUID

Below are instructions for subjects unable or unwilling to take whole, intact RP103 capsules and prefer to dose in liquid.

### OPTION 1 – ADMINISTRATION BY ORAL DOSING SYRINGE:

- Open all the capsules for either the morning or evening dose and sprinkle the contents into 4-6 ounces of an acceptable liquid.
- Mix gently for 5 minutes, then draw up the RP103-liquid mixture into a dosing syringe. Administer the entire dose by mouth. Do NOT administer the RP103-liquid mixture by G-tube.
- Eat the entire amount of RP103-food mixture. This may be followed by 8 ounces (1 cup) of an acceptable liquid.

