### **7.3. Study Drug Dosing Methodology**

Upon RP103-MITO-002 study entry, subjects will continue on the last total daily dose of RP103 taken during the previous RP103-MITO-001 study. Subsequent RP103 dose adjustments are permitted (e.g. as the subject grows, or if deemed necessary by the Investigator for tolerability reasons).

The Sponsor's medical officer may be consulted for assistance making RP103 dose adjustment decisions at any time during the study. NOTE: For each subject, when calculating the number of capsules to be taken every 12 hours (i.e. half of the prescribed total daily dose), if rounding is required to get a whole number of capsules to be taken, then rounding should be down and not up.

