### **9.5. Study Treatment Administration and Compliance**

Upon RP103-MITO-002 study entry, subjects will continue on the last total daily dose of RP103 taken during the RP103-MITO-001 study. Study drug labeled for the previous Study RP103-MITO-001 must be taken for the morning dose and associated PK blood draws on the day of Study Exit (which is also RP103-MITO-002 Day 1). Then, study drug labeled for Study RP103-MITO-002 is to be dispensed for the evening dose (RP103-MITO-002 Day 1) and - to be taken every 12 hours for the remainder of participation in Study RP103-MITO-002.

Detailed instructions for dosing are provided in Section 15.4 and subjects will also be provided with a handout with those same instructions. RP103 administered during study visits will be under the supervision of Investigator personnel.

A daily diary of protocol-specified medications will be maintained throughout the study and will be used to assess RP103 dosing compliance.

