#### 10.1.1. Day 1 (Baseline) Visit Procedures

- Obtain written consent, and assent if applicable
- Review data collected at the RP103-MITO-001 Study Exit Visit and review/confirm subject meets eligibility criteria for this extension study. If so, proceed with enrollment.
- The following study procedures can be carried forward from the RP103-MITO-001 Study Exit Visit and do not need to be duplicated:
  - Measure vital signs (blood pressure, heart rate, respiratory rate, and oral body temperature).
  - Measure height, body weight and head circumference; calculate BMI and BSA.
  - Perform physical examination.
  - Obtain a 12-lead ECG.
  - Administer age-specific NPMDS (only if not administered during RP103-MITO-001 Exit visit)
  - For each subject, perform the assessments associated with their preeminent symptoms already specified during Study RP103-MITO-001 (and detailed in Section 6.3.2 Secondary Endpoints).
  - Collect blood samples for laboratory tests, within 30 minutes before/after RP103 dose
  - Collect breath samples for hydrogen sulfide testing.
  - Collect and review seizure activity since the previous clinic visit. Dispense a paper seizure diary if applicable (or print from [www.seizuretracker.com](http://www.seizuretracker.com) website).
- For females, re-assess childbearing potential and menstrual history.
- The final dose of study drug labeled for the RP103-MITO-001 should have been taken that morning. Administer study drug labeled for RP103-MITO-002, with instructions to subject to take first dose of study drug for RP103-MITO-002 12 hours later than evening. Dispense RP103 for home administration. Explain and provide the subject and/or caregivers with RP103 Dosing Instructions.
- Provide subject and/or caregivers with re-training on the medications diary; dispense a blank diary for subjects to complete until the next study visit.
- Schedule or confirm the next study visit.

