### OPTION 2 – DRINKING:

- Open all the capsules for either the morning or evening dose and sprinkle the contents into 4-6 ounces of an acceptable liquid.
- Mix gently for 5 minutes in an uncovered cup, or – shake gently for 5 minutes in a covered cup (e.g., “sippy cup”). Drink all of the RP103-liquid mixture.

\* *The RP103-liquid mixture must be drunk or administered within 30 minutes after preparation.*

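### The oral-syringe dosing option ends by telling the subject to eat a food mixture that it never prepares, after the whole dose has been given as liquid

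*Protocol*

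**What the plan says.** Section 15.4 of the protocol gives four ways to take RP103 mixed with something else: two under Dosing in Food (eating, G-tube) and two under Dosing in Liquid (oral dosing syringe, drinking).

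The oral-syringe option first empties every capsule for the morning or evening dose into 4 to 6 ounces of liquid. After mixing and drawing up, its second step reads "Administer the entire dose by mouth. Do NOT administer the RP103-liquid mixture by G-tube". Its third and last step begins "Eat the entire amount of RP103-food mixture" and then allows an 8-ounce drink.

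The food mixture comes from the eating option, which says "Gently stir the medication beads into the soft food, creating an RP103-food mixture". The other liquid option ends its dosing step with "Drink all of the RP103-liquid mixture".

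On food timing, the same section says "Subjects should not eat for at least 2 hours before taking and at least 30 minutes after taking RP103". It allows about 4 ounces of food close to the dose only for subjects who cannot take RP103 without eating.

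These instructions are meant for use at home. Section 9.5 says "subjects will also be provided with a handout with those same instructions", and the Day 1 procedures in Section 10.1.1 tell staff "Explain and provide the subject and/or caregivers with RP103 Dosing Instructions".

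**The concern.** The last step of the oral-syringe option cannot be carried out as written. When the caregiver reaches it, every capsule for that dose has been opened, the whole dose has been swallowed, and there is no food mixture to eat.

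Because the text goes to families for twice-daily home dosing of children, the question is what a caregiver might do to comply. There are two wrong turns:

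- **Food too soon.** The caregiver gives food within the 30 minutes after the dose, to a subject who has no need of the food exception.
- **A repeat dose.** The caregiver opens a second set of capsules to make the food mixture, which doubles that administration.

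The planned compliance summary would not show a repeat dose. SAP Section 4.6.1 tabulates days with a missed dose, so an extra dose leaves that count unchanged.

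**Working it through.** The plan gives no figure to reproduce here. The check is a comparison of the instructions.

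**Step 1. What each option prepares and what it gives (Section 15.4).**

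| Option | Prepares | Gives | Match |
|---|---|---|---|
| Food 1, eating | food mixture | food mixture | yes |
| Food 2, G-tube | applesauce mixture | applesauce mixture | yes |
| Liquid 1, oral syringe | liquid mixture | liquid mixture, then names a food mixture | no |
| Liquid 2, drinking | liquid mixture | liquid mixture | yes |

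The mismatch is in 1 of 4 options and in 1 of the 3 steps of that option.

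**Step 2. Is it a carry-over?** The third step of the syringe option is word for word the closing step of the eating option, which is also where the term for the food mixture is introduced. That the line was copied across is an inference, but identical wording and a term with no antecedent support it strongly. The step is complete and sits among intact text, so it does not look like a redaction or a conversion fault.

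**Step 3. Could the food mixture be loose wording for the liquid mixture?** The protocol keeps the two apart: the food mixture must be used within 2 hours of preparation and the liquid mixture within 30 minutes. Even on the generous reading, the step would only repeat what the second step has already done.

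**Step 4. Is it corrected elsewhere?** Nothing in the rest of Section 15.4 or in the sections that refer to it does so.

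**Step 5. Effect on dose.** Section 7.3 sets each 12-hourly administration at "half of the prescribed total daily dose".

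- As written: all capsules for that administration, once, in liquid = 1 × the intended dose. Change in capsule count = 0.
- Worst case, if a second set is opened: 1 + 1 = 2 × the intended dose at that administration.

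Subjects' actual doses are not given. As an illustration, assume the cystinosis maintenance target of 1.30 g/m²/day in two doses (Section 5.2; Section 5.5 says the same doses are used here). Each administration is 1.30 / 2 = 0.65 g/m².

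- One administration doubled: 3 × 0.65 = 1.95 g/m² that day, which equals the maximum daily dose stated in Section 5.2.
- Both doubled: 4 × 0.65 = 2.60 g/m² that day.

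**Step 6. How often?** The documents give neither the number of syringe users nor any rate of misreading. The lower bound for both is 0.

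**The case against.** The strongest reply is that this is an editorial slip whose harm is conjectural. A caregiver who reads in order has opened every capsule for that dose and given all of it before meeting the stray line, and nothing in the option calls for a second set. The food risk is also modest: the stray line speaks of a drug-food mixture rather than plain food, the eating option itself uses about 4 ounces of soft food, and the documents quantify no effect of a little food after dosing.

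There are several safeguards. All subjects have completed RP103-MITO-001 and continue their last dose from it. Doses at visits are supervised. Diaries are reviewed at each visit, bottles come back quarterly, and drug accountability is checked. SAP Section 4.6.1 also requires a listing of every dosing event, and dosing violations are to be recorded and summarized (Protocol Section 12.6, SAP Section 3.2). Finally, the handout is not among the documents, and the study closed early (SAP Section 1.1).

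Most of this stands, and it limits the consequence. The doubled dose is a remote worst case. The diary, the listing and the deviation reports would show an extra dose only if someone recorded or noticed it; bottle returns could reveal sustained surplus use within about one visit interval, 3 months ± 7 days. The handout's wording cannot be checked, but Section 9.5 says that it carries the same instructions. None of these points makes the step correct.

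**Conclusion.** The concern holds. The final step of the oral-syringe option is wrong as written. It is a drafting error in operative dosing text, not a flaw in the design or the analysis.

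Its importance is low. The prescribed dose does not change, no planned statistical figure changes, and the likely result for most families is brief confusion. What remains is a small risk of food in the no-eating period or, remotely, of a doubled administration, with a frequency that the documents do not allow anyone to estimate and that may be zero. Reading the line as operative for home dosing assumes that the handout reproduces Section 15.4, as Section 9.5 says it does.

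**What to change.** Change the third step of Dosing in Liquid, Option 1 in one of two ways, depending on whether a follow-on drink is wanted. The documents do not settle this, and the parallel drinking option has none.

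- If a drink is wanted, replace the step with: *Give all of the RP103-liquid mixture. An optional drink of 8 ounces (1 cup) of a permitted liquid may follow.*
- If not, delete the step. The second step already completes the dose.

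Make the same correction in the subject handout before either text is reused. The cost is one line in each of the two texts, with no change to visits, data collection or analysis. Since the study has closed, no follow-up with sites is needed.

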### OPTION 2 – DRINKING:

- Open all the capsules for either the morning or evening dose and sprinkle the contents into 4-6 ounces of an acceptable liquid.
- Mix gently for 5 minutes in an uncovered cup, or – shake gently for 5 minutes in a covered cup (e.g., “sippy cup”). Drink all of the RP103-liquid mixture.

\* *The RP103-liquid mixture must be drunk or administered within 30 minutes after preparation.*

## ACCEPTABLE/UNACCEPTABLE FOODS AND LIQUIDS

### Acceptable soft foods for RP103 dosing:

Applesauce (not compote, not chunky), non-dairy pudding, or berry jelly.

### Acceptable liquids for RP103 dosing:

Fruit juice, e.g., orange juice (preferred), apple juice or any acidic fruit juice, PolyCitra, PolyCitra-K, non-caffeinated soda (allow bubbles to disperse so that soda is somewhat flat), or bottled or tap water with lemon concentrate added ( $\frac{1}{4}$  teaspoon concentrate per  $\frac{1}{4}$  ounce water / 1mL lemon concentrate per 7mL water).

### Unacceptable foods and liquids for RP103 dosing:

Milk, dairy products, alcoholic beverages, liquids or foods with a pH from neutral to basic (e.g., bottled or tap water without lemon concentrate added).

## 15.5. ADVERSE EVENTS CHECKLIST

The active ingredient in RP103 (cysteamine bitartrate) has been associated with CNS symptoms such as seizures, lethargy, somnolence, depression and encephalopathy which are common in this patient population. At each study visit (including the telephone visits at Week 2 and Week 6), subjects will be queried about the occurrence of these specific symptoms since the previous visit.

For each time point specified in the Schedule of Events (Protocol Section 2), the investigator or qualified designee will query the subject as to the presence or absence of the following symptoms. The interviewer should record the presence or absence of each adverse event in source documentation. Any positive response (present) must be assessed for relationship to underlying disease versus relationship to study drug.

- Skin rash
- Skin lesions
- Seizure
- Lethargy
- Somnolence
- Depression
- Encephalopathy
- Gastrointestinal ulceration and/or bleeding
- Nausea
- Vomiting
- Loss of appetite (anorexia)
- Diarrhea
- Fever
- Abdominal pain

## ABBREVIATIONS

Abbreviation	Definition
AE	Adverse events
ADL	Activities of Daily Living
BSA	Body Surface Area
BMI	Body Mass Index
CRF	Case Report Form
CSR	Clinical study report
CTCAE	Common Terminology Criteria for Adverse Events
ECG	Electrocardiogram
FARS	Friedreich Ataxia Rating Scale
FAS	Full Analysis Set
FDA	Food and Drug Administration
FRDA	Friedreich's Ataxia
GMFM	Gross Motor Function Measure
ICH	International Conference on Harmonisation
INR	International Normalized Ratio
LHON	Leber's Hereditary Optic Neuropathy
MedDRA	Medical Dictionary for Regulatory Activities
NPMDS	Newcastle Pediatric Mitochondrial Disease Scale
NYHA	New York Heart Association
PT	Preferred Term
ROS	Reactive Oxygen Species
SAE	Serious Adverse Event
SAF	Safety Analysis Set
SAP	Statistical analysis plan
SOC	System Organ Class
TEAE	Treatment-Emergent Adverse Event
WHO	World Health Organization
6MWT	6-Minute Walk Test
8MW	8-Minute Walk
9-HPT	9-Hole Peg Test

